### 2.5.4 Definition Of Datasets

For the statistical analysis the enrolled Subjects will be divided into the following datasets:

	Study Title	An Interventional, Post-Market Study to Evaluate the Performance of a Custom-made Medical Device, "Breast Cancer Locator Guidance (BCL)" System, in Breast-conserving Surgery (BCS)		
	Study ID	CS-BCL-EU2021	Sponsor	CairnSurgical Inc.
	Date	25Nov2022	Version	1.0 Substantial Amendment 1_GERMANY

Safety Analysis Set (SAS):	The "Safety Set" included all enrolled patients undergoing surgery with the BCL System.
Full Analysis Set (FAS):	The "Full Analysis Set" (FAS): this set included all enrolled patients undergoing surgery with the BCL System.
Per-Protocol Set (PPS):	The "Per-Protocol Set (PPS)" would include all the FAS patients who (a) met all inclusion/exclusion criteria liable to affect the performance assessment, (b) did not present serious deviations of the protocol that may affect efficacy.

Definition of major protocol deviations and selection of Subjects accordantly will be performed prior to database lock.

## 2.5.5 Handling Of Missing Values Including Withdrawals

Handling of missing data will be described in detail in the SAP. If nothing is described no imputation of data will be carried out in case of missing data, but all available data will be used to its full extent. Patients who withdraw from the study will not be replaced. The end of the study will occur when the last participating patient completes the last scheduled visit of the Investigational plan.

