	
enroll patients who require the tumor to be localized in order for the surgeon to perform BCS. The investigation will be useful to collect Investigational Product (IP)' performance/safety evidence in Europe.
 
Each Subject, after signing the Informed Consent Form (ICF), will enter into a screening phase (V0) during which several assessments (e.g., demographics, medical history, evaluation of available prone MRI and core biopsy pathological results) will be conducted. Blood samples will be collected at V0.
 
At visit 1 (V1), the Subject will undergo supine MRI (10-40 days prior to surgery), from which the 3D breast image and BCL will be made. At visit 2 (V2) the patient will undergo BCS using the BCL system.
 
Soon after surgery and prior discharge, potential AEs will be assessed. On the same day, the specimen volume will be determined. The excised specimen will be sent to the pathological lab for analysis. The results, including the positive margin rate (PMR) and specimen mammogram, will be obtained within 14 days.
 
At visit 3 (V3), follow-up assessments (including physical examination, and AEs review) will be performed. At the End Of Study (EOS/V4), AEs events will be assessed and patients will be asked to express their satisfaction with the BREAST-Q.
		
Study Population:	Adult women with a diagnosis by pre-operative biopsy of non-palpable breast cancer.		
Number of subjects (planned and analysed):	Planned:	35 subjects will be enrolled.	
	Sample size justification:	
The positive margin rate (PMR) rate with the use of BCL is expected to be < 5%. If we assume a true PMR rate of 3% and applying the exact or Clopper-Pearson method for a single binomial proportion then a sample size of N=35 will achieve a confidence interval with total width of 15%.
 
We will calculate an exact binomial confidence interval using the actual PMR.
	
	Safety Set	The "Safety Set" included all enrolled patients undergoing surgery with the BCL system.	
	Full Analysis Set (FAS)	The "Full Analysis Set" (FAS): this set included all enrolled patients undergoing surgery with the BCL system.	
	Per protocol Set (PPS)	The "Per-Protocol Set (PPS)" would include all the FAS patients who (a) met all inclusion/exclusion criteria liable to affect the performance assessment, (b) did not present serious deviations of the protocol that may affect efficacy.	

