## 2.5 STATISTICAL METHODS AND DATA ANALYSIS

### 2.5.1 Sample Size Justification

The positive margin rate (PMR) rate with the use of BCL is expected to be < 5% based on our previous study [20]. If we assume a true PMR rate of 3% and applying the exact or Clopper-Pearson method for a single binomial proportion then a sample size of N=35 will achieve a confidence interval with total width of 15%. The upper limit of this confidence interval (18%) is lower than the currently observed positive margin rate using the standard of care.

We will calculate an exact binomial confidence interval using the actual PMR.

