### 2.5.2 Data Analysis

In general, all the variables will be descriptively analysed by visit (mean, median, standard deviation, minimum and maximum for continuous variables after normality check of distribution with Kolmogorov-Smirnov test, frequency distribution for categorical variables).

In particular, for the primary analysis PMR will be calculated when results of histopathological examination will be provided (results will be available within 14 days from the day of sample arrival at the pathological lab).

Moreover, 95% Confidence Interval (CI) of PMR will be presented.

All secondary endpoints will be evaluated in a descriptive way presenting the results by study visit, where appropriate.

All the analysis will be detailed in the Statistical Analysis Plan (SAP) which will be finalized in Version 1.0 before the Data Base Lock (DBL).

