## 2.6 PATIENT SELECTION CRITERIA

All Patients shall be screened for initial study eligibility by the Principal Investigator or his/her designees at the investigational site. Potential candidates, that according to the Investigator judgment should undergo BCS with the BCL, will be identified, with the assessment of their eligibility criteria, by the study site Principal Investigator and research staff.

Patients will be considered to be enrolled in the study once they have met all of the inclusion and none of the exclusion criteria. Patients who do not meet the criteria will not be enrolled in the study.

The patient involvement in the study will last until the EOS visit.

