### 1.2.3. Sample Size

The positive margin rate (PMR) with the use of BCL is expected to be < 5% based on a previous study [2]. Assuming a true PMR of 3% and applying the exact or Clopper-Pearson method for a single binomial proportion then a sample size of N=35 patients who have undergone surgery with the BCL and have had a margin assessment will achieve a confidence interval with total width of 15%. The upper limit of this confidence interval (18%) is lower than the currently observed positive margin rate using the standard of care.

An exact binomial confidence interval will be calculated using the actual PMR. The withdrawal of patients before the surgery with BCL will be considered as drop-out.

Statistical power calculation was performed using SAS® software [1], version 9.4.

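### The protocol plans 35 enrolled without replacement, while the SAP attaches the same 15% interval width to 35 operated and assessed patients, so the SAP's N is reached only with zero loss

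*Protocol*

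**What the plan says.** **Protocol, 25 November 2022.**
- The synopsis states that "35 subjects will be enrolled".
- Section 2.6 fixes when a patient counts: "Patients will be considered to be enrolled in the study once they have met all of the inclusion and none of the exclusion criteria". The flowchart (2.10.3) places this check at V0, before the supine MRI (V1) and surgery (V2).
- Section 2.5.5 adds: "Patients who withdraw from the study will not be replaced".
- Section 2.5.4 restricts the full analysis set to enrolled patients who are operated with the BCL System.
- Section 2.5.1 gives the precision argument: "If we assume a true PMR rate of 3" percent, then "applying the exact or Clopper-Pearson method for a single binomial proportion", a sample size of "N=35 will achieve a confidence interval with total width of 15" percent. It also gives an upper limit of 18% and says that this lies below the rate seen with standard of care. It does not say whether the 35 are enrolled or evaluable patients.

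**SAP, version 0.1, 26 November 2024.**
- Section 1.2.3 gives the same assumption, method, width and upper limit, but defines the number: "N=35 patients who have undergone surgery with the BCL and have had a margin assessment will achieve a confidence interval".
- The same section classes a withdrawal before BCL surgery as a drop-out. It gives no rate, no inflation of 35 and no replacement rule.
- Section 1.1 names its source as version 2.0 of the protocol, dated 21 November 2023. That version is not among the documents supplied.

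**The concern.** The number 35 has two meanings. In the protocol it is the planned enrolment, reached at V0. In the SAP it is the number operated and assessed. With no replacement and no allowance, the two agree only if every enrolled patient is operated and has a margin result.

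Loss between the two points is foreseeable from the plan itself. Screening may be up to 30 days before the MRI, and surgery follows 10-40 days after it. In between, the images must be obtained and transferred, and the device made and shipped. The SAP's collected variables include reason fields for a supine MRI not done, images not transferred, surgery not performed, and a specimen not removed or not sent to pathology.

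Two things are at stake. A site or monitor cannot tell from these documents whether enrolment ends at 35 eligible or 35 evaluable patients. And the planned precision, which with the upper limit is the whole sample-size argument, is stated for a number that the enrolment rule does not secure.

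**Working it through.** **Inputs.** Assumed true rate 3% and exact Clopper-Pearson method (protocol 2.5.1, SAP 1.2.3). N=35 (both documents). Confidence level 95%, taken as two-sided; section 2.5.1 does not state it, but 2.5.2 does: "Moreover, 95% Confidence Interval (CI) of PMR will be presented". No drop-out rate is given anywhere.

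**Formula.** For x positives among n patients, the lower limit is the 2.5% quantile of Beta(x, n − x + 1) and the upper limit is the 97.5% quantile of Beta(x + 1, n − x). The width is the difference.

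**Reproducing the plan's figure.** At n=35 the expected count is 0.03 × 35 = 1.05.
- With x = 1.05 the interval is 0.09% to 15.14%, width 15.05 points.
- With the nearest whole count, x = 1, it is 0.07% to 14.92%, width 14.84 points.

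Both round to the stated 15%. Other readings fit less well: at 90% confidence with x = 1 the width is 12.7 points, and for a 3% rate the Wald and Wilson 95% intervals give 11.3 and 14.2.

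**Stated upper limit.** The exact upper limit at n=35 is 14.9% to 15.1%, not 18%. The figure 18 equals 3 + 15, which is what results if the full width is added to the point estimate.

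**Effect of losses from 35** (percentage points; upper limit in %):

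| n | losses | width, x = 1 | width, x = 0.03n | upper limit, x = 1 |
|---|---|---|---|---|
| 35 | 0 | 14.84 | 15.05 | 14.92 |
| 34 | 1 | 15.25 | 15.34 | 15.33 |
| 33 | 2 | 15.68 | 15.64 | 15.76 |
| 32 | 3 | 16.14 | 15.96 | 16.22 |
| 30 | 5 | 17.13 | 16.65 | 17.22 |
| 29 | 6 | 17.68 | 17.02 | 17.76 |
| 28 | 7 | 18.26 | 17.42 | 18.35 |

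The first loss adds 0.3 to 0.4 points and the width still rounds to 15. The second brings it to 15.6-15.7, which rounds to 16. Seven losses are 7/35 = 20%, the upper end of an assumed 0-20% range.

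**Chance of zero loss.** If each patient were lost independently with probability d (assumed), the chance that all 35 are evaluable is (1 − d)^35: about 49% at d = 2% and 17% at d = 5%.

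**Enrolment needed for 35 evaluable**, 35/(1 − d) rounded up: 37 at 5%, 39 at 10%, 42 at 15%, 44 at 20%.

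**Against the count of positives.** At n=35 the width is 10.0 with no positives, 14.8 with one and 18.5 with two. One further positive moves it by 18.5 − 14.8 = 3.7 points, about the same as losing seven patients with x = 1 (18.3 − 14.8 = 3.5).

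**The case against.** The strongest objection is about versions. The SAP rests on protocol V2.0, a year later than the protocol in hand, and visible differences show that the plan moved on. The SAP has six centres against three, two more secondary objectives, and analysis sets that no longer say enrolled. Its definition of the 35 may come straight from V2.0. A reader might take SAP section 7, which declares no change from the protocol and its amendments, as confirming the conflict. It does not: for this SAP the reference is V2.0, and the declaration if anything suggests that V2.0 agrees with the SAP. This stands. The mismatch is shown only between the two documents supplied.

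A reader might also infer that the 15% width fails at the first patient lost. At the whole-percent precision the documents use, it does not. A strict 15.00 limit cannot have been meant, since x = 1.05 already gives 15.05 at n=35.

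Nor is precision the only property claimed. Both documents also state an 18% upper limit, and with one positive the exact limit stays below 18% down to n=29. The study is descriptive with no test or success threshold, and the reported interval will use the observed rate. With no positives, which has probability 0.97^35, about 34%, the width is 12.3 points even at n=28.

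Finally, the synopsis gives 35 as a plan and does not call it a maximum. All this limits the consequence. It does not remove the double meaning of 35 or the missing drop-out allowance.

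**Conclusion.** The point holds as a defect in sample-size accounting, of modest size. On the documents supplied, 35 enrolled at eligibility without replacement yields the SAP's 35 operated and assessed patients only with zero loss, and neither document allows for loss. At the planning value of one positive margin, the rounded width passes 15% from the second loss and reaches about 17 points at 30 patients and 18 at 28.

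This assumes a two-sided 95% level and one positive, or 3% of n. The 0-20% range of loss is my assumption. The documents do not support a claim that the study misses a criterion, because none is set, or that the governing protocol contradicts the SAP, because V2.0 cannot be seen. The 18% upper limit is a separate arithmetic error in the same paragraph of both documents and does not depend on losses.

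**What to change.** First check what V2.0 says on enrolment and replacement. Then use one definition of N=35 in the synopsis, protocol 2.5.1 and 2.5.5, and SAP 1.2.3. Two versions are coherent:

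1. **35 means operated with the BCL and assessed.** Limit the no-replacement sentence in 2.5.5 to withdrawals after surgery, so that patients lost earlier are replaced, and say how an operated patient without a margin result is counted. Alternatively, raise planned enrolment for an explicit drop-out rate.
2. **35 means enrolled, without replacement.** State the expected width as about 15-18 points for 35 down to 28 evaluable patients, and label the 0-20% loss as an assumption.

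In either case, change the 18% upper limit to about 15% at N=35 in both documents.

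The cost is a few sentences, plus a few more enrolments under the first option: two at 5% loss (37 − 35), four at 10% (39 − 35). The SAP is dated November 2024 and describes surgery in the past tense. If recruitment has closed, only the wording can change: settle the definition before database lock and report how many enrolled patients were not operated or not assessed.

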## 2.6 PATIENT SELECTION CRITERIA

All Patients shall be screened for initial study eligibility by the Principal Investigator or his/her designees at the investigational site. Potential candidates, that according to the Investigator judgment should undergo BCS with the BCL, will be identified, with the assessment of their eligibility criteria, by the study site Principal Investigator and research staff.

Patients will be considered to be enrolled in the study once they have met all of the inclusion and none of the exclusion criteria. Patients who do not meet the criteria will not be enrolled in the study.

The patient involvement in the study will last until the EOS visit.

### 2.6.1 Inclusion Criteria

- Patient Informed consent form (ICF) signed;
- Female Aged  $\geq 18$  years at the time of the signature of ICF;
- Histologic diagnosis of IBC or DCIS;
- Tumor excision that will require localization because it cannot be definitively defined by palpation;
- The tumor is unifocal; possible satellite lesions  $< 2$  cm from primary are eligible;
- The tumor enhances and is greater than or equal to 5mm on prone breast MRI imaging;
- Subject and surgeon agree to perform BCS;
- Willingness to follow all study procedures, including attending all site visits, tests and examinations.

	Study Title	An Interventional, Post-Market Study to Evaluate the Performance of a Custom-made Medical Device, "Breast Cancer Locator Guidance (BCL)" System, in Breast-conserving Surgery (BCS)		
	Study ID	CS-BCL-EU2021	Sponsor	CairnSurgical Inc.
	Date	25Nov2022	Version	1.0 Substantial Amendment 1_GERMANY

## 2.6.2 Exclusion Criteria

- Absolute contraindication to MRI, including presence of implanted electrical device (e.g., pacemaker or neurostimulator), aneurysm clip, or metallic foreign body in or near eyes;
- Severe claustrophobia;
- Contraindication to use of gadolinium-based intravenous contrast, including life-threatening allergy;
- Uncontrolled cardiac, renal, or pulmonary disease;
- Uncontrolled systemic disease (e.g., lupus erythematosus or scleroderma);
- Compromised renal function including chronic, severe kidney disease (GFR < 30 ml/min/1.73m^2), or acute kidney injury;
- Pregnancy or breast-feeding (\*);
- Subjects who have received or plan to receive neoadjuvant chemotherapy;
- Sternal notch to nipple distance of > 32 cm as measured in a sitting or standing position;
- Measurement of widest circumference around breasts and arms > 135 cm;
- Known allergy to device components;
- Multicentric tumors (additional tumors > 2 cm from primary);
- Infectious or inflammatory processes near the area of intervention;
- Planned surgery with localization devices including WGL, intraoperative ultrasound guidance, radiofrequency emitting implants, magnetic seeds, radioactive seeds, and tissue inspection devices;
- Simultaneous participation in an interventional study or participation in an interventional study in the last 1 month before study inclusion, that, in the opinion of the Investigator, could impact patient's safety or the study endpoints;
- Known drug and/or alcohol abuse;
- Mental incapacity that precludes adequate understanding or cooperation.

*(\*) The pregnancy status will be assessed by performing urine pregnancy test (dipsticks will be provided by the Investigational site).*

*Women not of childbearing potential may have undergone menopause or permanent sterilization (hysterectomy, bilateral oophorectomy, or bilateral tubal ligation). Menopause is defined as ≥12 months of non-therapy-induced amenorrhea. Hysterectomy, bilateral oophorectomy, or bilateral tubal ligation must be documented.*

*Women of childbearing potential must agree to complete abstinence from sexual intercourse or to use single or combined contraceptive methods that result in a failure rate of <1% per year from 6 days prior to administration of the study product until completion of the study. Abstinence is only acceptable if it is in line with the preferred and usual lifestyle of the patient. Alternatively, established, proper use of combined oral or injected hormonal contraceptives, or double barrier method (condom used with spermicidal foam or occlusive cap used with spermicidal foam) from 6 days prior to administration of the study product until completion of the study are acceptable.*

	Study Title	An Interventional, Post-Market Study to Evaluate the Performance of a Custom-made Medical Device, "Breast Cancer Locator Guidance (BCL)" System, in Breast-conserving Surgery (BCS)		
	Study ID	CS-BCL-EU2021	Sponsor	CairnSurgical Inc.
	Date	25Nov2022	Version	1.0 Substantial Amendment 1_GERMANY

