### 1.2.2 General Description

The BCL System is a patient-matched Breast Conserving Surgery (BCS) guidance device derived from *supine* breast magnetic resonance imaging (MRI) data. The device allows the surgeon to transfer surgical cues associated with a patient's breast and breast cancer to help guide the surgeon with the tumor resection procedure.

The BCL is created using an additive manufacturing (3D printing) process involving a digital model that is derived from the Subject's *supine* MRI data.

The BCL model is constructed from a biocompatible, semi translucent, UV-cured, photopolymer resin material using the stereolithography (SLA) additive manufacturing process.

The BCL System is comprised of the following components and accessories:

- BCL Kit, including:
  - Sterile patient-specific BCL model
  - BARD® GHIATAS® Beaded Breast Localization Wires (up to 6, patient-specific sizes; sizes are limited to 5 cm, 7 cm, 9 cm, or 14 cm)
  - Medical grade permanent marking pen and ruler (Viscot Medical, LLC Sterile Reg/Fine Tip XL Prep Resistant Ink Marker)
- MR Kit, including:
  - Viscot Medical, LLC Sterile Reg/Fine Tip XL Prep Resistant Ink Marker (x1)
  - 3M™ Tegaderm™ Transparent Dressing (x3)
  - Izi Medical Products MRI fiducial markers (x5)
- MR Coil Pad Kit, including:
  - MRI Coil Cushion (pad) (x2)

	Study Title		An Interventional, Post-Market Study to Evaluate the Performance of a Custom-made Medical Device, "Breast Cancer Locator Guidance (BCL)" System, in Breast-conserving Surgery (BCS)	
	Study ID	CS-BCL-EU2021	Sponsor	CairnSurgical Inc.
	Date	25Nov2022	Version	1.0 Substantial Amendment 1_GERMANY

The BCL device itself doesn't contain any software. However, various software tools are used to design the BCL:

- Combination of commercial off the shelf (COTS) software and proprietary CairnSurgical software components to create digital anatomical models of the Subject's breast surface, tumor, chest wall, the BCL device model, and patient-specific reports of geometrical data to relevant to BCS.
- An optional web browser-based interactive surgical plan Visualizer will be provided. The Visualizer software displays the 3D model of the BCL, the tumor, and chest wall, with visual markers to show locations where the tumor is closest to the skin and closest to the underlying chest wall/muscle (including distances from tumor to skin and the tumor to the chest wall).

[figure not shown]

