#### Notes:

A Informed Consent Form (ICF) signed and dated, before any trial procedure is performed. In order to provide the Investigator with an adequate time frame to organize and perform the clinical tests and assess the inclusion/exclusion criteria on the Subject, the screening phase was set up a maximum duration of 30 days (V0). After the ICF is signed, a supine MRI will be scheduled as soon as possible but according to local standard procedure.

B Medical history includes patient-reported bra cup size and documentation of any contraindications to MRI (e.g., implanted electrical devices exist), history of adverse reactions to gadolinium, breastfeeding or pregnancy.

C Physical examination includes weight, height, distance from sternal notch to the nipple, the circumference around the breast and arms, calculation of BMI, and specific documentation that the breast cancer cannot be palpated.

D Laboratory Tests include:

- serum creatinine levels to calculate the glomerular filtration rate (GFR), acid uric for renal dysfunction;
- complete blood count;
- electrolytes (sodium, potassium, chloride, bicarbonate).

E For females of childbearing potential only, urine pregnancy test will be performed with dipsticks supplied by the Investigator. Results must be available before any procedure.

F All Subjects will have had a mammogram and prone MRI assessment prior to enrollment. If breast ultrasound images are obtained, they will be available to the study team. The results from pathologic analysis of diagnostic core biopsy specimens, including IBC vs. DCIS, will be documented. Results of imaging studies should be obtained within 3 months of study enrollment.

G After the tumor specimen is removed:

- the specimen volume will be determined by water displacement,
- a specimen mammogram will be obtained and then the specimen will be sent to the pathologist for evaluation of the positive margins.

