#### 2.10.4 Visit 0 (V0): Screening (within 15-30 days before V1)

- Signed and dated Informed Consent obtained prior to start any procedure scheduled for the study;
- Verification and confirmation of the inclusion/exclusion criteria;
- Medical history;
- Demographics (including age, smoking habits and alcohol use);
- Vital signs (BP, HR, O2 saturation);
- Physical examination;
- Blood samples (laboratory parameters);
- Urine pregnancy test to all women of childbearing potential;
- Evaluation of radiological assessment;
- Adverse Events;
- Concomitant medications.

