#### 2.10.5 Visit 1 (V1): Supine MRI (Day 0)

- Vital signs (BP, HR, O2 saturation);
- Supine MRI;
- Adverse Events;
- Concomitant medications;
- Device deficiencies/incidents monitoring.

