### 5.4. Visit Windows

In the study, 5 study visits were planned.

- The screening/baseline visit will be performed within 30 days before V1
- V1 will be performed at day 0
- V2 will be performed within 10/40 days from V1
- V3 will be performed at week 2  $\pm$  7 days from V2
- EOS visit will be performed after 6 weeks since V2  $\pm$  7 days.

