### 6.1.2. Demographic and Other Baseline Characteristics

#### Collected Variables:

- Age (years) [CRF – V0]
- Ethnic group (Caucasian/Asian/Black/Other) [CRF – V0]
- If Other, please specify (free text) [CRF – V0]
- Smoking habits (Non-smoker/Former smoker/Smoker/Smoker with medical device) [CRF – V0]
- Alcohol abuse (Yes/No)
- If Yes, please specify (free text) [CRF – V0]
- Was urine pregnancy test performed? (Yes, No, Menopausal status, Surgery for sterility, Other) [CRF – CRF – V0]
- If no, please specify (free text) [CRF – V0]
- If Other, please specify (free text) [CRF – V0]
- If Yes: Date of pregnancy test (dd/mmm/yyyy) [CRF – V0]
- Result of pregnancy test (Positive/Negative) [CRF – V0]

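### The only scheduled pregnancy test can be 30 days old at the study's gadolinium MRI, and the contraception rule need not cover the days in between

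*Protocol*

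**What the plan says.** **Exclusion and risk.** Protocol 2.6.2 excludes pregnant women. Section 2.11.3 names pregnant patients among the groups that might be at higher risk from gadolinium retention.

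**Test.** The V0 list (Protocol 2.10.4) has the entry "Urine pregnancy test to all women of childbearing potential". The V1 list (2.10.5), which is the contrast MRI visit, has none, and the flowchart agrees. Note E to the flowchart adds "Results must be available before any procedure", without a maximum age for the result or a repeat. The SAP shows the same single test at V0 (flow chart in 1.2.5; collected variables in 6.1.2).

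**Interval from test to MRI.** The protocol labels V0 as 15-30 days before V1. Note A says "the screening phase was set up a maximum duration of 30 days (V0"), which is only an upper limit. SAP 5.4 says "The screening/baseline visit will be performed within 30 days before V1", also with no lower limit.

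**Contraception.** The footnote to Protocol 2.6.2 requires abstinence or effective contraception "from 6 days prior to administration of the study product until completion of the study". Neither document says which event counts as administering a device made up of imaging accessories, a printed form and wires.

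**The concern.** The study itself imposes the contrast MRI at V1. Two rules are meant to keep a pregnant woman from reaching it: a test that shows she is not pregnant, and contraception that keeps this true. They protect her only if contraception begins no later than the test, or if the test is repeated at exposure. The plan requires neither, so a woman can test negative at V0, conceive before contraception becomes mandatory, and receive gadolinium with the exclusion recorded in good faith as not met.

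What is at stake is participant safety. The primary analysis is not touched: the FAS contains patients who had surgery with the BCL System (SAP 4.1), and nothing here alters the PMR or its interval.

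**Working it through.** The plan gives no figure of its own to reproduce, so the check is day arithmetic with V1 as day 0.

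**Inputs**
- t = days from the V0 test to V1: 15 to 30 by the protocol label (2.10.3, 2.10.4); 0 to 30 by SAP 5.4.
- s = days from V1 to V2: 10 to 40 (Protocol 2.10.6).
- Contraception starts 6 days before product administration (Protocol 2.6.2).

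**Which event is administration?** Two readings are possible.
- *V1, the better supported.* In Protocol 1.2.2, "The BCL System is comprised of the following components and accessories" introduces a list that includes the MR Kit and coil pads. Section 1.3 packs them with the study product, and SAP 6.4.5 records device deficiencies during product use at V1 as well as V2.
- *V2, the weaker.* Section 1.3.1 ties the subject's product accountability form to the date of surgery.

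**V1 reading.** Contraception starts on day -6. Uncovered days = max(0, t - 6).
- Protocol label: 15 - 6 = 9 to 30 - 6 = 24.
- SAP window: 0 (whenever t is 6 or less) to 24.

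**V2 reading.** Contraception starts s - 6 days after the MRI: 10 - 6 = 4 to 40 - 6 = 34. All t days before contrast are uncovered.
- Protocol label: 15 to 30.
- SAP window: 0 to 30.

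| Reading | Window | Contraception starts | Uncovered days from test to MRI |
|---|---|---|---|
| V1 | Protocol, t = 15-30 | day -6 | 9-24 |
| V1 | SAP, t = 0-30 | day -6 | 0-24 |
| V2 | Protocol, t = 15-30 | day +4 to +34 | 15-30 |
| V2 | SAP, t = 0-30 | day +4 to +34 | 0-30 |

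Within the protocol's own window the gap is at least 9 days on either reading. It vanishes only if V0 may fall within 6 days of V1 and administration means V1, or if the test is done on the day of the MRI.

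**Does other text close the gap?** Note E does not, because a V0 result of any age satisfies it. The footnote accepts abstinence only where it is the woman's usual lifestyle, and asks for established use of hormonal methods. But its first sentence also accepts any method with a failure rate below 1% per year, without asking that it be established, so a woman who starts such a method on day -6 complies. Protocol 2.9 lets the investigator withdraw a subject from a harmful procedure, but that presupposes the pregnancy is known. The mitigation section, 2.11.5, deals with gadolinium allergy and renal function and does not mention pregnancy.

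**The case against.** The strongest case against has four parts.

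1. *On the V1 reading the rule does reach the MRI.* Contraception is in force on the day, a negative test is on file, and only an earlier stretch is uncovered. That is correct, and the larger V2 figures should not carry the weight. But contraception in force at the MRI does not reveal a pregnancy that began between V0 and day -6.
2. *Other safeguards exist.* Protocol 2.11.5 has subjects interviewed about adherence at scheduled visits, and V1 is one. Medical history covers pregnancy. The imaging procedures, the instructions for use and local practice may include a check before contrast. An adherence interview, however, cannot detect non-use on days when contraception is not yet required. Checks in documents that were not available may exist, but nothing in the protocol or SAP requires a retest.
3. *The affected group may be tiny and the harm unproven.* The number of women of childbearing potential among the planned 35 is not given, and Protocol 2.11.3 says no adverse clinical consequences of retention have been proven. This stands and limits the severity. Still, women aged 18 and over are eligible, and the sponsor wrote a contraception rule for those who could conceive.
4. *The text may be out of date.* The clause comes from the amendment of 25 November 2022, whereas the SAP rests on protocol V2.0 of 21 November 2023. The SAP, dated 26 November 2024, describes surgery partly in the past tense, so few patients may remain to benefit. This also stands. The V2.0-based SAP confirms the V0-only test but says nothing about the contraception wording.

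**Conclusion.** The concern holds. The one scheduled test can be up to 30 days old at contrast, and the contraception rule does not reach back to it. On the better-supported V1 reading, 9 to 24 days are uncovered in the protocol's window and 0 to 24 in the SAP's. On the weaker V2 reading, the whole interval is uncovered. This should be corrected as a safety rule that falls short of the exposure it is meant to guard. It has no bearing on N=35 or the PMR analysis.

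Confidence is medium. The conclusion assumes that the contraception clause survives unchanged in protocol V2.0 and that no imaging document used at the sites already requires a test before contrast. The day counts are window extremes; how many women would fall in the gap cannot be estimated from the documents.

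**What to change.** First check whether protocol V2.0 has already reworded the clause. If it has not:

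- **Protocol 2.6.2, footnote, both occurrences:** start the contraception requirement at the V0 pregnancy test instead of 6 days before product administration. This removes the undefined term and by itself brings the uncovered interval to 0 days.
- **Protocol 2.10.3 and 2.10.5:** keep the V0 test for eligibility and add a urine test at V1 for women of childbearing potential, with a negative result required before contrast is given. The site already supplies the dipsticks.
- **SAP 1.2.5 and 6.1.2:** add the V1 test, its date and its result.

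**Cost.** A short protocol and consent amendment, and one dipstick and one CRF entry for each woman concerned. The contraception commitment lengthens in the protocol window by 9 to 24 days on the V1 reading. On the V2 reading it lengthens by t + s - 6 days: 15 + 10 - 6 = 19 to 30 + 40 - 6 = 64. The sample size and the primary analysis do not change.
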